## **5. SAFETY ASSESSMENTS**

Safety data will be summarized for the safety population.

Adverse events will be coded by system organ class and preferred term according to the Medical Dictionary for Regulatory Activities (MedDRA). Severity of AEs will be graded by the investigator according to the National Cancer Institute-Common Terminology Criteria for Adverse Events (NCI-CTCAE) v4.0 for non-hematological AEs and iwCLL 2008 guidelines for hematologic toxicity.

Treatment-emergent adverse events (TEAE) are all reported AEs from the first dose of the study drug, through the treatment phase and up to 30 days after the last dose of the study drug or initiation of subsequent anticancer therapy, whichever came first. TEAE SAEs, TEAE non-SAEs and TEAE leading to death will be summarized by treatment arm.

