	
Descriptive statistics for change in scores from baseline to each assessment will be summarized for the PROs assessed by the FACiT-Fatigue. Time to hematological improvement will be compared using unstratified log rank test. Percentage of patients achieving hematological improvement will be compared using the chi-square test.
 
Exploratory Efficacy Analysis:
 
PFS and ORR as determined by the Investigator will be summarized and analyzed similarly to PFS and ORR as determined by the IRC. Percentage of patients achieving improvement/or resolution in disease-related symptoms will be compared using chi-square test.
 
Descriptive statistics for change in scores from baseline to each assessment will be summarized for the PROs assessed by EORTC QLQ-C30 and EQ-5D-5L.
 
Descriptive statistics will be provided for parameters collected for medical resource utilization associated with the therapy.
 
Safety Analysis:
 
Detailed tabulations of safety data (adverse events [AEs] and clinical laboratory tests) will be provided for all patients receiving the study drug. The number and percent of patients with treatment-emergent AEs will be summarized. Summary of other safety parameters by treatment group will be provided where appropriate.

Interim Analysis	
One interim analysis using the Lan-DeMets alpha spending function based on O'Brien-Fleming boundary for both superiority and futility (non-binding) will be conducted after observing approximately 117 PFS events. Futility will be evaluated by a one-sided test. The DMC will review and evaluate efficacy and safety results.

Sample Size Determination	
With the agreement from the European (Rapporteur and Co-Rapporteurs) and US Health Authorities, the overall two-sided significance level for this study is revised from 0.01 to 0.05. Given this revision in overall significance level, 176 PFS events provides approximately 90% power to detect the target hazard ratio of 0.6 based on a log-rank test and a two-sided overall significance level of 0.05 adjusted for one planned interim analysis.

TABLE OF CONTENTS

PROTOCOL APPROVAL PAGE	2
SYNOPSIS.....	3
TABLE OF CONTENTS	9
LIST OF TABLES	14
LIST OF FIGURES	15
LIST OF APPENDICES	15
LIST OF ABBREVIATIONS AND DEFINITIONS	16
1. INTRODUCTION.....	20
1.1. Ibrutinib.....	20
1.1.1. Mechanism of Action of Ibrutinib.....	21
1.1.2. Cellular Selectivity of Ibrutinib.....	21
1.2. Summary of Nonclinical Data	22

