4. STUDY DESIGN

This is a randomized, multicenter, open-label, Phase 3 study designed to evaluate the safety and efficacy of ibrutinib as compared to ofatumumab in patients with relapsed or refractory CLL/SLL who have failed at least one prior line of therapy and are not considered appropriate candidates for treatment or retreatment with purine analog based therapy.

Eligible patients will have been diagnosed with CLL/SLL and have relapsed or refractory disease following at least 1 line of prior systemic therapy for CLL/SLL.

A minimum of 350 patients will be randomized in a 1:1 ratio to receive either ofatumumab (Treatment Arm A) or ibrutinib (Treatment Arm B).

The site will enter eligibility data into an Interactive Web Response System (IWRS) prior to randomization.

Randomization will be used to minimize bias in the assignment of patients to treatment groups, to increase the likelihood that known and unknown patient attributes (eg, demographic and baseline characteristics) are evenly balanced, and to enhance the validity of statistical comparisons across treatment groups. Two randomization schemes will be generated: one for each geographic region (North America versus Rest of World). Under each scheme, patients will be randomized based on the following two stratification factors:

- Presence versus absence of disease refractory to purine analog and anti-CD20 containing chemoimmunotherapy regimen
- Presence versus absence of 17p del, as defined by the assay specification on pretreatment fluorescence in situ hybridization (FISH) or cytogenetics evaluation

Patient participation will include a Screening Phase, a Treatment Phase, and a Follow-up Phase.

The Screening Phase will be up to 28 days prior to first dose of study drug, during which the patient's eligibility and baseline characteristics will be determined.

The Treatment Phase will extend from randomization until study drug discontinuation. Patients randomized to ofatumumab will receive treatment for up to 6 months per the package insert. Patients randomized to ibrutinib will receive study drug daily until disease progression or unacceptable toxicity. Further information on dosing is provided in [Section 6](#). Regularly scheduled disease assessments are required throughout the Treatment Phase.

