6. TREATMENTS

Patients will be randomized 1:1 to either Treatment Arm A or B.

Treatment Arm A: Ofatumumab IV

Treatment is 12 IV doses over 24 weeks or until disease progression, unacceptable toxicity, or the patient meets any criteria specified in [Section 10](#), whichever occurs first. Administration of ofatumumab will be in accordance with the manufacturer's package insert.

Treatment Arm B: Ibrutinib PO

Treatment is 420 mg (3 x 140-mg capsules) administered orally daily to continue until disease progression, unacceptable toxicity, or the patient meets any criteria specified in [Section 10](#), whichever occurs first.

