6.1.2. Dose Delay

Treatment with ofatumumab should be held for any unmanageable, potentially study drug-related toxicity that is Grade 3 or greater in severity. Additional information concerning dose delays can be found in Section 6.1.4.

Any other clinically important events where dose delays may be considered appropriate by the investigator must be discussed with the Medical Monitor.

Study drug may be held for a maximum of 28 days from expected dose due to toxicity. Study treatment should be discontinued in the event of a toxicity lasting > 28 days, unless reviewed and approved by the Medical Monitor.

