12.9.1. Adverse Events (AEs)

Adverse events (AEs) will be graded by the Investigator according to the NCI CTCAE v4.0 for non-hematological AEs. Hematologic toxicity will be assessed by the IWCLL 2008 criteria for grading hematologic toxicity in CLL studies. Verbatim descriptions of AEs will be coded using the current version of the Medical Dictionary for Regulatory Activities (MedDRA). Adverse events that started from the date of the first dose of study drug up to 30 days after the date of the last dose of study drug are considered treatment-emergent. All-treatment emergent AEs will be summarized by treatment arm. The incidence rates of treatment-emergent AEs will be summarized by System Organ Class (SOC), preferred term, toxicity grade, and relationship to study drug. In addition, SAEs, Grade 3 or above AEs, AEs leading to study treatment discontinuation, delay, reduction, or interruption, AEs leading to death, and events of special interest will be summarized. Multiple occurrence of the same event in a given patient will be counted once at the maximum severity and strongest relationship to study drug.

AEs leading to death and non-fatal SAEs will be listed by patient and tabulated by preferred term.

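### The final-analysis AE tables would compare percentages of patients over a window of about 28 weeks on ofatumumab and an open-ended one on ibrutinib, with no common-window or person-time table planned

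*SAP*

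**What the plan says.** SAP section 5, which governs the final analysis of the November 2018 extract, gives one sentence on presentation: "TEAE SAEs, TEAE non-SAEs and TEAE leading to death will be summarized by treatment arm". It does not say whether the summary is a percentage, a rate or something else.

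The measure comes from the protocol. The synopsis states: "The number and percent of patients with treatment-emergent AEs will be summarized". Section 12.9.1 states: "The incidence rates of treatment-emergent AEs will be summarized by System Organ Class", followed by other breakdowns. The word rates there does not imply person-time. No time denominator is given, and the counting rule is: "Multiple occurrence of the same event in a given patient will be counted once at the maximum severity and strongest relationship to study drug". That is a proportion of patients.

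Treatment length differs by design. For ofatumumab (Protocol section 6): "Treatment is 12 IV doses over 24 weeks or until disease progression, unacceptable toxicity". For ibrutinib (Protocol section 4): "Patients randomized to ibrutinib will receive study drug daily until disease progression or unacceptable toxicity". The synopsis puts the end of the study about 5 years after the last enrolment. SAP section 5 closes the treatment-emergent window 30 days after the last dose, or at the start of subsequent anticancer therapy if that is earlier.

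Protocol section 12.9 plans a descriptive summary of drug exposure. Neither document plans AE rates per unit of patient-time, a time-to-first-event analysis, or an AE table limited to the same period in both arms.

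**The concern.** Comparing safety and tolerability between the arms is a stated secondary objective (Protocol 3.2) and endpoint (11.2). A percentage of patients ever having an event rises with time at risk. When one arm is watched for about half a year and the other possibly for several years, a by-arm percentage mixes toxicity with length of observation. With equal toxicity, ibrutinib would look worse. With unequal toxicity, a reader could not tell how much of the difference came from the drug. The final analysis is more exposed to this than an early one, because ibrutinib time can keep accruing after ofatumumab windows have closed.

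**Working it through.** **Ofatumumab window.** Protocol 6.1.1.2 gives doses at week 1, weeks 2 to 8, and weeks 12, 16, 20 and 24: 1 + 7 + 4 = 12, which reproduces the stated 12 doses. Adding 30 days gives 23 + 4.3 = 27.3 weeks if the last dose falls 23 weeks after the first, and 24 + 4.3 = 28.3 weeks if 24. Protocol 6.1.2 adds: "Study drug may be held for a maximum of 28 days from expected dose due to toxicity". One such hold gives 32.3 weeks. Three holds (Table 1 of section 6.1.4 allows a restart after each of the first three occurrences) give 40.3.

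**Ibrutinib window.** There is no fixed length. Exactly 1 year on drug plus 30 days is 56.5 weeks, or 2.0 times 28.3.

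**Illustration.** Assume the same constant rate r of first events in both arms. The percentage affected over t years is 1 − exp(−r·t), averaged over t where t varies. Inputs:
- Ofatumumab, full course: (168 + 30)/365.25 = 0.542 years.
- Ofatumumab stopping at progression: median PFS 5.8 months, the midpoint of 5.7 and 5.9 in Protocol 2.2, so the hazard is ln2/(5.8/12) = 1.434 per year. The share reaching 24 weeks is exp(−1.434 × 0.460) = 52%; the mean window is 21.9 weeks.
- Ibrutinib A, design hazard ratio 0.6 (Protocol 12.3): 0.6 × 1.434 = 0.860 per year, capped at 5 years, mean 1.15 years, plus 30 days.
- Ibrutinib B: exactly 1 year plus 30 days.
- Ibrutinib C, 12-month PFS of 88% (Protocol 1.3.2.1) held for 5 years: −ln(0.88) = 0.128 per year, mean 3.7 years, plus 30 days.

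At r = 0.10, ofatumumab gives 1 − exp(−0.0542) = 5.28% for a full course, or 4.09% when stopping at progression. Ibrutinib gives 11.06% (A), 10.26% (B) and 30.42% (C). Ratios of ibrutinib to ofatumumab percentages:

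| Events per patient-year | Full course: A / B / C | Stops at progression: A / B / C |
|---|---|---|
| 0.05 | 2.2 / 2.0 / 6.3 | 2.8 / 2.5 / 8.2 |
| 0.10 | 2.1 / 1.9 / 5.8 | 2.7 / 2.5 / 7.4 |
| 0.20 | 2.0 / 1.9 / 4.9 | 2.5 / 2.4 / 6.3 |
| 1 | 1.4 / 1.6 / 2.1 | 1.7 / 2.0 / 2.7 |
| 2 | 1.1 / 1.3 / 1.4 | 1.4 / 1.6 / 1.7 |

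**Sensitivity at r = 0.10, full course.** One hold in every ofatumumab patient: 1.8 (A), 5.1 (C). Three holds in every patient: 1.5 (A), 4.1 (C). Case C with an assumed extra 0.1 or 0.2 per year stopping ibrutinib for other reasons (mean 3.0 or 2.5 years): 4.8 or 4.0.

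**In patients.** With 175 per arm (350 randomised 1:1) and r = 0.10, about 9 ofatumumab patients have the event against 19 (A) or 53 (C). The crude ratio is 2.1 (95% CI 0.98 to 4.5) or 5.8 (3.0 to 11.2), from identical toxicity.

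**Would person-time rates cure it?** Only if the hazard is roughly constant. Suppose both arms share a hazard of 0.4 per year for the first 0.542 years and 0.1 afterwards. Ofatumumab's first-event rate is 0.4. With an ibrutinib window of 1.15 years, 24.2% have the event over 0.962 years at risk per patient: rate 0.252, ratio 0.63. With 3.7 years, 41.3% over 2.667 years: rate 0.155, ratio 0.39. Equal toxicity then appears as an advantage for ibrutinib.

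**Common window.** Limit both arms to 24 weeks plus 30 days, let both stop at progression, and take r = 0.10. The ratio of percentages falls to 1.10 (A) or 1.26 (C).

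**The case against.** The strongest reply is that this is a descriptive section of a late analysis. No test or decision rule uses these tables. The DMC recommended that the interim analysis serve as the primary analysis, and its study report was completed in March 2014. Exposure is to be summarised, so a reader will see the imbalance. SAP section 5 is brief and does not rule out adjusted rates. The illustration also rests on assumed inputs: case A implies a 12-month ibrutinib PFS of exp(−0.860) = 42%, far from the 88% behind case C, and the ofatumumab medians come from fludarabine-refractory patients, a narrower group than this trial admits.

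Most of that is right, and it limits the point. What survives is that an exposure summary shows the imbalance without correcting any event comparison, and that a plan silent on measure falls back on the protocol's percentages. The direction of the distortion needs no assumed input beyond equal rates and a longer ibrutinib window.

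Three stronger readings are tempting and not supported:
- A reader might infer that the trial's main safety comparison was distorted. The plan behind the 2014 analysis is not among the documents, so nothing can be said about it.
- A reader might infer that patient-year rates would settle the matter with a ratio centred on 1. That needs a constant hazard. Protocol 2.2 says infusion-related events decrease after the first infusion, and with early-clustered events a whole-period rate ratio is biased towards ibrutinib.
- A reader might infer that events after crossover inflate the ofatumumab arm, because Protocol 12.9.1 does not end the window at subsequent therapy. SAP section 5 does, and SAP Table 1 treats next-line ibrutinib as subsequent therapy. That wording difference adds no weight here.

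**Conclusion.** The gap is real and worth closing, as an improvement to how a stated secondary comparison is read. It does not threaten the primary conclusion. If event rates were equal and constant, percentages for uncommon events (0.05 to 0.20 per patient-year) would be about 2 to 3 times higher on ibrutinib with about 1 year of treatment, and about 4 to 8 times higher with about 2.5 to 4 years. Dose holds in every ofatumumab patient would pull the lower end down to about 1.5. For very common events (2 per patient-year) the ratio is about 1.1 to 1.7.

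These sizes rest on assumed rates, exponential time to stopping and PFS figures borrowed from the protocol's background and design sections. Cases A and C are brackets, not forecasts. Early-onset events such as infusion reactions do not follow the model.

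**What to change.** In SAP section 5, name the measure and keep the percentages of patients over the whole treatment-emergent period. Then add:

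1. As the main by-arm comparison, a table limited to the first 24 weeks plus 30 days in both arms, with person-time shown, for all TEAEs, SAEs, grade 3 or higher events, fatal events and events of special interest. Protocol 12.9.1 already names these classes ("In addition, SAEs, Grade 3 or above AEs, AEs leading to study treatment discontinuation", and so on).
2. As a supplement, first-event rates per 100 patient-years by arm, preferably split into the first 28 weeks and later. Label them as valid for comparing arms only if the hazard is roughly constant.

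The cost is SAP wording and a few tables from data already collected. Three limits should be stated. If ofatumumab patients stop early at progression, the common window still leaves a ratio of about 1.1 to 1.3, which is why its person-time must be shown. Later ibrutinib events have no on-treatment ofatumumab counterpart after a course given on schedule, so they can largely only be described. Rate ratios for uncommon events are imprecise: at 0.10 per year, exp(±1.96 × √(1/9.2 + 1/19.4)) spans 0.46 to 2.2 around a ratio of 1.
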